3.5. Coding Dictionaries

Medical history, medical or surgical procedures, and AEs will be coded using Medical Dictionary for Regulatory Activities (MedDRA) Version 25.0 or higher.

Prior and concomitant medications will be coded using World Health Organization (WHO) Drug Dictionary March 2022.

Adverse events and laboratory values will be classified as mild, moderate, or severe.

3.6. Stratified Analysis

Efficacy analyses will be stratified by biomarker status and region. Details are presented under the analysis for each endpoint.

3.7. Testing Hypotheses and Multiple Comparisons

All statistical tests for the treatment comparison of efficacy endpoints will be based on a 1-sided alpha level of 0.05. For each endpoint, the null hypothesis is that the effects of each of the two liafensine treatment arms and placebo are the same. The alternative hypothesis is that liafensine is better than placebo.

As illustrated in Figure 2, the family-wise Type I error rate will be controlled at a fixed 1-sided alpha level of 0.05 using a closed testing procedure for multiple dose comparisons and multiple endpoint comparisons in DGM4-positive patients (Marcus 1976). In the closed testing procedure, the average effect of liafensine 1 mg and 2 mg dose groups will be first compared with the placebo group on change in MADRS total score from baseline to Day 42 in DGM4-positive patients. If the 1-sided p-value was ≤ 0.05 , then the 1-sided p-values are calculated for the comparisons of 1 mg dose vs placebo and 2 mg dose vs placebo, respectively. If both individual p-values are ≤ 0.05 , a significant treatment effect is declared for the corresponding dose group. All

other efficacy endpoints will not be controlled for multiplicity with nominal p-values provided for the exploratory purpose only.

Figure 2. Statistical Testing Procedure

*All tests are based on 1-sided alpha of 0.05.

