## **8.3.3.1.** Type I Error Control for Multiple Comparisons

The family-wise type I error rate will be controlled at a fixed 1-sided alpha level of 0.025 using a closed testing procedure for multiple dose comparisons and multiple endpoint comparisons in DGM4-positive patients (Marcus 1976). In the closed testing procedure, the average effect of 1 mg and 2 mg dose groups will be first compared with the placebo group on change in MADRS total score from baseline to Day 42 in DGM4-positive subjects. If the one-sided p-value was  $\leq 0.025$ , then the one-sided p-values are calculated for the comparisons of 1 mg dose vs placebo and 2 mg dose vs placebo, respectively. If both individual p-values are  $\leq 0.025$ , a significant treatment effect is declared for both dose groups. If only one p-value is  $\leq 0.025$ , a significant treatment effect is declared for the corresponding dose group. All other efficacy endpoints will not be controlled for multiplicity with nominal p-values provided for the exploratory purpose only. Additional details will be specified in the SAP.

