1.2.2. Secondary Endpoints

Key Efficacy Endpoint:

• Change in CGI-S from baseline to Day 42, in DGM4-positive patients

Safety Endpoints:

- Adverse events (AEs) as characterized by type, frequency, severity, timing, seriousness, and relationship to study therapy
- Laboratory abnormalities as characterized by type, frequency, severity, and timing
- Vital signs including supine (after at least 5-min rest) and standing (after 1-min and 3-min standing), blood pressure (BP) and heart rate (HR), weight, electrocardiogram (ECG), clinical laboratory evaluation, Discontinuation-Emergent Signs and Symptoms (DESS) scale, and Columbia-Suicide Severity Rating Scale (C-SSRS) data

Other Secondary Efficacy Endpoints:

- CGI-I at Day 42, in DGM4-positive patients
- Change in SDS from baseline to Day 42, in DGM4-positive patients

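### Family-wise error control is claimed for multiple endpoints, but the testing procedure covers only MADRS and gives the key secondary CGI-S no route to a controlled claim

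*SAP*

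**What the plan says.** SAP 3.7 states that "the family-wise Type I error rate will be controlled at a fixed 1-sided alpha level of 0.05", by means of a "closed testing procedure for multiple dose comparisons and multiple endpoint comparisons in DGM4-positive patients". Protocol 8.3.3.1 claims the same scope at a different level: "The family-wise type I error rate will be controlled at a fixed 1-sided alpha level of 0.025". SAP Table 4 records the change of level.

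The procedure has two stages. First, "the average effect of liafensine 1 mg and 2 mg dose groups will be first compared with the placebo group on change in MADRS". If that test succeeds, "then the 1-sided p-values are calculated for the comparisons of 1 mg dose vs placebo and 2 mg dose vs placebo, respectively". Both stages concern MADRS at Day 42 in DGM4-positive patients.

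The protocol paragraph then adds: "All other efficacy endpoints will not be controlled for multiplicity with nominal p-values provided for the exploratory purpose only". SAP 3.7 repeats this: "other efficacy endpoints will not be controlled for multiplicity with nominal p-values provided".

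SAP 1.2.2 lists as the key efficacy endpoint "Change in CGI-S from baseline to Day 42, in DGM4-positive patients". SAP 5.4.2 gives CGI-S a model (MMRM without imputation) but no gate, alpha share or place in a test order. SAP 4.1 and 5.4 also give it sensitivity analyses alongside the primary endpoint, in the randomized and per-protocol sets.

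**The concern.** One paragraph makes two statements that cannot both be true: error is controlled over several endpoints, and every endpoint except MADRS is uncontrolled. The protocol leaves further details to the SAP, but the SAP adds nothing on endpoints. SAP Table 4 does not mention the matter, so the gap is not a recorded decision.

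Two things are at stake. A pre-specified statement about error control is untrue as written and could pass unchanged into the study report. And CGI-S, ranked above the other secondary endpoints, has the same inferential standing as response rate or a single MADRS item. If pooled MADRS and both doses succeed, the trial still cannot make a controlled statement on its key secondary endpoint.

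**Working it through.** **Inputs.** From SAP 2.3: 47 DGM4-positive patients per arm, 1:1:1 allocation, difference 4.5, SD 9 (0.5 SD), 80% power at two-sided 0.05. From SAP 3.7: one-sided alpha 0.05. From Protocol 8.3.3.1: one-sided alpha 0.025. Assumed: MADRS/CGI-S correlation ρ of 0.6 to 0.9, and normal test statistics with equal variances.

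**1. The plan's own sample size.** For pooled active versus placebo (2:1), n per arm = 1.5 × [9 × (1.960 + 0.842) / 4.5]² = 47.09. With 47, SE = 9 × √(1/47 + 1/94) = 1.608, and 4.5/1.608 = 2.799. Power is Φ(2.799 − 1.960) = 79.9%. The stated 47 and 80% reproduce.

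**2. Control across doses on MADRS.** This was simulated with three arms of 47, testing the pooled contrast first and then each dose, all at one-sided 0.05.
- No effect at either dose: probability of any false rejection 0.050.
- One dose null, the other effective by 0.25 to 3 SD: 0.046 to 0.050.

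The dose half of the claim holds.

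**3. Adding CGI-S with no gate.** Under the complete null, P(at least one false positive on pooled MADRS or pooled CGI-S) = 2α − P(both), where P(both) is the bivariate normal upper-tail probability at correlation ρ.

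| One-sided α | ρ | P(both) | P(at least one) |
|---|---|---|---|
| 0.05 | 0.6 | 0.0155 | 0.084 |
| 0.05 | 0.7 | 0.0196 | 0.080 |
| 0.05 | 0.9 | 0.0319 | 0.068 |
| 0.025 | 0.6 | 0.0062 | 0.044 |
| 0.025 | 0.9 | 0.0148 | 0.035 |

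If all three CGI-S contrasts were read this way, simulation gives about 0.10 to 0.12 at one-sided 0.05.

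**4. Error control with CGI-S placed last.** Suppose any MADRS null is true. CGI-S is reached only after that null has been wrongly rejected, so an error is already counted and the CGI-S test adds none. Suppose instead that every MADRS null is false. The only possible error is then the CGI-S test itself, at level α. Family-wise error therefore stays at α or below. Simulation at one-sided 0.05 agrees: 0.050 under the complete null, and 0.048 to 0.050 with MADRS effective at 0.5 SD and CGI-S null.

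**5. How often that gate opens.** For one dose against placebo, SE = 9 × √(2/47) = 1.857, and 4.5/1.857 = 2.424.
- One-sided 0.05: power per dose Φ(2.424 − 1.645) = 78.2%.
- One-sided 0.025: power per dose Φ(2.424 − 1.960) = 67.9%.

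The two dose statistics share the placebo arm and have correlation 0.5. Both succeed with probability about 66% at 0.05 and 53% at 0.025. When both succeed, pooled MADRS must also succeed: Z(pooled) = (Z₁ + Z₂)/√3, which is at least 1.15 times the critical value. The gate therefore opens 66% or 53% of the time.

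If CGI-S also had a 0.5 SD effect with ρ = 0.7 (both assumptions), it would succeed under control about 64% of the time at 0.05 and 50% at 0.025.

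**The case against.** The best defence is that the plan resolves its own ambiguity. The sentence making all other endpoints nominal is specific and appears in both documents, so an analyst would report CGI-S as nominal. The primary objective is to demonstrate superiority, whereas the CGI-S objective is only to evaluate. This is a Phase 2b study, and SAP Table 4 says it was not powered for multiplicity-adjusted testing of each dose. Leaving CGI-S uncontrolled is a legitimate choice, and deleting the stray words would be purely editorial.

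Most of this stands. A reader might infer that the trial has no family-wise control, or that its error rate is really 7% to 8%. The documents support neither. The MADRS dose comparisons are controlled, and the inflated figures describe only a confirmatory reading of CGI-S that the plan disclaims.

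It is also fair that the proposed gate is demanding and that the SAP is already at a version submitted shortly before database lock. Gating on pooled MADRS alone would open more often (about 88% at one-sided 0.05, 80% at 0.025). But CGI-S would then run beside the dose tests, each at full alpha. If one dose and CGI-S were both null, two unprotected chances of error would remain unless alpha were split.

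The defence does not remove the contradiction. The claim of control over endpoints is still in both documents, and together with the key secondary label it invites the reading that the last sentence rules out.

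**Conclusion.** The point holds as a gap between the stated and the delivered scope of error control. Control across doses on MADRS is sound, and the primary test is unaffected. Control across endpoints is claimed but absent, and CGI-S cannot support a controlled claim under the plan as written.

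The sizes in step 3 are conditional: they apply only if a nominal CGI-S p-value is treated as confirmatory, and they rest on the assumed correlation. The finding also rests on the text and on the footnote to SAP Figure 2, because the diagram itself was not available. It should be confirmed that the diagram shows no CGI-S step.

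**What to change.** Before unblinding, add one final step: pooled CGI-S versus placebo, tested at the same alpha only if pooled MADRS and both MADRS dose tests succeed. If the gate does not open, CGI-S stays nominal. Four edits follow:
- exempt CGI-S from the sentence that leaves all other endpoints uncontrolled;
- align Protocol 8.3.3.1 with SAP 3.7;
- update SAP Figure 2;
- add an entry to SAP Table 4.

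MADRS loses no power, because CGI-S comes last. The cost is the document work and a gate that, under the plan's own assumptions, stays closed about one time in three at one-sided 0.05 and nearly half the time at 0.025.

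If the sponsor prefers CGI-S to stay nominal, delete the words *and multiple endpoint comparisons* from Protocol 8.3.3.1 and SAP 3.7. That changes no analysis. It is also the only remedy left once the data are unblinded.

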3.8. Assessments

3.8.1. Montgomery-Åsberg Depression Rating Scale

Montgomery-Åsberg Depression Rating Scale (MADRS) is a 10-item clinician-administered scale, designed to be particularly sensitive to antidepressant treatment effects in patients with major depression (Montgomery 1979). Each MADRS item is rated on a 0 to 6 scale. The MADRS total score is calculated as the sum of the 10 individual item scores; the total score can range from 0 to 60. Higher MADRS scores indicate higher levels of depressive symptoms.

3.8.2. Clinical Global Impressions Scale-Severity

Clinical Global Impressions Scale-Severity (CGI-S) asks the clinician one question: "Considering your total clinical experience with this particular population, how mentally ill is the patient at this time?" which is rated on the following seven-point scale: 1 = normal, not at all ill; 2 = borderline mentally ill; 3 = mildly ill; 4 = moderately ill; 5 = markedly ill; 6 = severely ill; 7 = among the most extremely ill patients (Guy 1976).

This rating is based upon observed and reported symptoms, behavior, and function in the past seven days. Clearly, symptoms and behavior can fluctuate over a week; the score should reflect the average severity level across the seven days.

3.8.3. Clinical Global Impressions Scale-Improvement

Clinical Global Impressions Scale-Improvement (CGI-I) is similarly simple in its format (Guy 1976). Each time the patient is seen after medication has been initiated, the clinician compares the patient's overall clinical condition to the one-week period just prior to the initiation of medication use (the so-called baseline visit). The CGI-S score obtained at the baseline (initiation) visit serves as a good basis for making this assessment. Again, only the following one query is rated on a seven-point scale: "Compared to the patient's condition at admission to the project (prior to medication initiation), this patient's condition is: 1 = very much improved since the initiation of treatment; 5 = minimally worse; 6 = much worse; 7 = very much worse since the initiation of treatment."

The CGI-I score generally tracks with the CGI-S such that improvement in one follows the other. Anchors for scoring, however, are quite different, and the CGI-I is based upon changes from the initiation of treatment in contrast to changes from the preceding week of treatment. Consequently, the two CGI scores can occasionally be dissociated such that a clinician may notice changes in the CGI-I relative to baseline despite no recent changes in the overall CGI-S score or vice versa.

3.8.4. Sheehan Disability Scale

Sheehan Disability Scale (SDS) is used to assess functional impairment in three major life domains: work, social life/leisure activities, and family life/home responsibilities (Sheehan 2008). It is a five-item scale that will be completed by the participant. Three items use a Likert scale with a 10-point range (0 / Moderately to 10 / Extremely) and two items are openended (eg, "On how many days in the last week did you...?").

The first three items assess disruption of (1) work (2) social life/leisure activities, and (3) family life/home responsibilities using a 0-10 rating scale. The scores for the first three items are summed to create a total score of 0-30 where a higher score indicates greater impairment. It also has one item on days lost from school or work and one item on days when underproductive.

3.8.5. Columbia-Suicide Severity Rating Scale

Columbia-Suicide Severity Rating Scale (C-SSRS) was designed to quantify the severity of suicidal ideation and behavior (Posner 2011). C-SSRS is a measure used to identify and assess individuals at risk for suicide. Questions are phrased for use in an interview format but can be completed as a self-report measure if necessary. C-SSRS measures four constructs: the severity of ideation, the intensity of ideation, behavior, and lethality. It includes "stem questions," which if endorsed, prompt additional follow-up questions to obtain more information. There are four versions of the scale available, including: 1) Baseline/screening version, which allows practitioners to gather a lifetime and recent 12 months history of suicidal ideation and/or behavior; 2) Since Last Visit version for assessment of suicidal thoughts and behaviors since C-SSRS was last administered; 3) Screen version, a shortened version of the full form (3-6 questions) most commonly used in clinical triage settings; 4) Risk Assessment Page, which provides a checklist of protective and risk factors of suicidality.

3.8.6. Discontinuation-Emergent Signs and Symptoms Scale

Discontinuation-Emergent Signs and Symptoms Scale (DESS) is used to monitor patients for discontinuation symptoms (Rosenbaum 1998). It includes 43 signs or symptoms for which the patient indicates whether there has been any change since their last visit – indicating new symptom, old symptom but worse, old symptom but improved, old symptom but unchanged, symptom not present. The DESS total score on a given day is calculated as the count of items with new symptoms or old symptoms but worse over all 43 items. For missing items, it will be imputed as the average from the non-missing items. The total score can range from 0 to 43. The number and proportion of subjects with the sum of zero, 1, 2, 3, and ≥ 4 will be presented each day and by the treatment arm. Treatment comparison will be performed each day from Day 1 to Day 14 using the Cochran-Mantel-Haenszel (CMH) test stratified by region and biomarker status. The average DESS total score over the assessment period will be calculated for each subject and compared between treatment group using the Wilcoxon rank-sum test.

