- e Baseline evaluations will be performed on Day -1. Patients will be instructed to take the first dose of double-blind study drug the day after baseline evaluations (ie, on Day 1), and will be instructed to take double-blind study drug for the remainder of the 6-week treatment period.
- f For patients who discontinue early from the study, safety and efficacy determinations designated for Day 42 will be performed on the last day the patient takes a full dose of study drug or as soon as possible thereafter, but within 3 days of their last dose in any event.
- g At Visit 1, two brief ICFs will be obtained for the purpose of genotyping and biobanking, separately. A full ICF must be obtained at Visit 2.
- h Refer to Appendix 2 Preliminary Diagnosis Checklist
-  A separate blood sample (6 mL) will be collected for PGx (eg, determination of DGM4 status at Screening and for future research at Visit 5).
- The PRDF Checklist must be completed by the patient and reviewed by the rater 2 prior to CGI-S assessment. The baseline checklist entry must be compared by rater 2 against post-baseline entry to refresh the knowledge of patient's baseline condition prior to CGI-I assessment.
- k C-SSRS baseline/screening version
-  C-SSRS since-last-visit version
- m For randomized patients who complete the study or discontinue early, the DESS scale will be completed daily by the patient for 14 days post-last dose.
- n Vital signs should be taken prior to blood draws when applicable and include supine (after at least 5 min rest) and standing (after 1 min and 3 min standing), BP and heart rate, respiration rate, and temperature. Vital signs can be repeated for up to 3 occurrences after Visit 2 to see if values return to normal range, but any abnormality must be resolved by the Baseline Visit.
- o ECG recordings will be completed prior to blood draws when applicable and will be performed in triplicate (at 1-minute intervals between each of the three recordings) for baseline. Single ECG will be performed for rest of the timepoints.

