3.9.3. Handling of Missing Data for MADRS

For MADRS, the total score is set to missing for any patient if 50% or more items are missing at an assessment. If less than 50% of items are missing, the missing items will take the average from the non-missing items. These calculated total scores will not be rounded to whole numbers.

Missing data for the total score of MADRS will be maintained as missing unless specified otherwise.

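### SAP 3.8.6 mean-fills missing DESS items but tabulates whole-number totals, so some symptomatic days fit no category, and it sets no minimum number of answered items

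*SAP*

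**What the plan says.** All of the scoring rules stand in one paragraph, SAP 3.8.6.

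- **Definition.** The daily total is "calculated as the count of items with new symptoms or old symptoms but worse over all 43 items".
- **Missing items.** "For missing items, it will be imputed as the average from the non-missing items".
- **Range.** "The total score can range from 0 to 43".
- **Table.** "The number and proportion of subjects with the sum of zero, 1, 2, 3, and ≥ 4 will be presented each day", by treatment arm.
- **Daily test.** "Treatment comparison will be performed each day from Day 1 to Day 14 using the Cochran-Mantel-Haenszel (CMH) test", stratified by region and biomarker status. The response variable is not named.
- **Period average.** Each subject's mean total over the assessment period is "compared between treatment group using the Wilcoxon rank-sum test".

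The source is a self-completed diary: Protocol Table 1, footnote m, has it that "the DESS scale will be completed daily by the patient for 14 days post-last dose".

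SAP 5.5.4 only refers back to 3.8.6. The DESS description in Protocol 7.6.1.5 has no missing-item rule, and Protocol 8.3.4 leaves missing safety data unimputed unless the protocol or SAP says otherwise. For MADRS, SAP 3.9.3 sets a floor: "the total score is set to missing for any patient if 50% or more items are missing at an assessment". It also says that prorated MADRS totals stay unrounded. SAP 3.9.4 covers the other efficacy scales, not the DESS. SAP 3.1 requires category percentages, with missing data counted, to total 100%.

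**The concern.** The definition, the fill rule and the category list do not fit together. A count is a whole number, but filling a blank with a mean makes it a fraction, and the list has no place for fractions between 1 and 4. A day totalling 3.07 is neither missing nor in a category, so a table programmed literally cannot total 100% as SAP 3.1 requires. The days exposed are those with one to three symptoms; a symptom-free day stays at exactly 0 however many items are blank. If such days were left out and one arm had more of them, the table would understate that arm's symptoms.

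The second gap is the missing floor. The SAP will not score a MADRS assessment with half its items blank, but it will extrapolate a DESS day from a single answer.

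The DESS is a named safety endpoint (Protocol 2.2.3, SAP 1.2.2) and the dedicated measure of discontinuation symptoms. Protocol 1.2.1 presents a low potential for such symptoms as a possible advantage of the drug.

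**Working it through.** **Inputs.** There are 43 items (SAP 3.8.6). Let k be the number endorsed (new or worsened, scored 1; otherwise 0) and m the number blank. Each blank takes the mean of the answered items, k/(43 − m). The total is

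T = k + m × k/(43 − m) = 43k/(43 − m).

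**1. The stated range.** With k = 0, T = 0. With every answered item endorsed, k = 43 − m and T = 43. Enumerating m = 0 to 42 with every possible k gives a minimum of 0 and a maximum of 43. The SAP's range is reproduced and never exceeded.

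**2. When T is a whole number.** Because 43 is prime, with at least one blank T is a whole number only if k = 0 or every answered item is endorsed. Every other day with a blank has a fractional total.

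**3. One blank (m = 1), T = 43k/42.**

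| k | T | Category |
|---|---|---|
| 0 | 0 | 0 |
| 1 | 1.02 | none |
| 2 | 2.05 | none |
| 3 | 3.07 | none |
| 4 | 4.10 | ≥ 4 |

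**4. How many blanks keep a day outside the categories.** T must be below 4.

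- k = 1: 1 to 32 blanks (43/11 = 3.91; at 33 blanks, 43/10 = 4.3)
- k = 2: 1 to 21 blanks (86/22 = 3.91; at 22 blanks, 86/21 = 4.10)
- k = 3: 1 to 10 blanks (129/33 = 3.91; at 11 blanks, 129/32 = 4.03)

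Beyond these limits the day moves into ≥ 4. One endorsed item among ten answered counts as 4.3.

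**5. No floor.** One answered item gives 0 or 43. One endorsed of three answered gives 43/3 = 14.33. The inflation factor 43/(43 − m) can reach 43. Under the MADRS 50% rule at most 21 items could be blank, and the factor would stop at 43/22 = 1.95. The floor alone does not close the category gaps: k = 1 with 1 to 21 blanks still gives 1.02 to 1.95.

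**6. Share of patient-days affected.** The documents give no item-missing rate q and no mean symptom count λ, so both are assumed. Blanks are taken as independent with probability q, and each answered item as endorsed with probability λ/43. The share is the sum, over all (m, k) that fall in a gap, of Bin(m; 43, q) × Bin(k; 43 − m, λ/43).

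| λ | q = 0.5% | 1% | 2% | 5% |
|---|---|---|---|---|
| 0.5 | 7.5% | 13.5% | 22.2% | 33.5% |
| 1 | 11.8% | 21.4% | 35.3% | 53.4% |
| 2 | 14.2% | 25.8% | 42.7% | 65.5% |
| 3 | 12.0% | 21.7% | 36.1% | 56.3% |
| 5 | 5.1% | 9.2% | 15.5% | 25.3% |

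At q = 1% the range is about 9% to 26%; over the whole grid it is about 5% to 66%. If the diary does not allow blanks, it is zero.

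**The case against.** The strongest reply is that this is a binning detail in one descriptive safety table. A programmer would notice that the percentages do not reach 100% and would round or re-bin. Fractional totals are normal under proration, and the SAP accepts them openly for MADRS. All DESS data are also listed (SAP 5.5.4), so no report disappears. Much of this stands, and it limits the point. The SAP does not say that such days are dropped; that is only what a literal reading of the category list produces.

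Several stronger readings are tempting, and the documents do not support them.

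- **That days fall out of both tests.** The Wilcoxon test uses each subject's average and takes fractions as they are. The CMH test loses days only if it is run on the categories, which the SAP does not state. The sample code in SAP 8.8, written for a Visit 7 endpoint, uses the analysis value; run that way on the DESS total, every fractional day stays in.
- **That scores are impossible.** No total leaves 0 to 43. A 43 from one answer is implausible, but it is within range.
- **That sparse days dominate the Wilcoxon test.** One spurious 43 among 14 days adds at most 43/14 = 3.07 to one subject's mean, and that subject still contributes one rank.
- **That the DESS is the only source on these symptoms.** Adverse events are recorded through follow-up (Protocol 7.6.2.7), and events within 30 days of the last dose count as treatment-emergent (SAP 5.5.1).
- **That the chance of any blank is the share of days lost.** That chance, 1 − (1 − q)^43, is 19%, 35%, 58% and 89% at q = 0.5%, 1%, 2% and 5%. A day is uncategorised only if it also has one to three endorsed items, which gives the lower figures in the table.

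What the reply does not remove is that the rule, followed as written, gives totals with no category and sets no floor. The SAP leaves the choice of repair to discretion, and the possible repairs differ: one endorsed item with 15 blanks is 1 as an observed count but 43/28 = 1.54, hence 2, when rounded.

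**Conclusion.** The point holds in limited form. Days with one to three endorsed items and at least one blank either fit no planned category or, with many blanks, are inflated into ≥ 4. Days with none, or with four or more, always fit. With no floor, a day can be scored from a single answer. The daily table is affected, and the CMH test conditionally; the Wilcoxon test is affected only through the missing floor.

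The arithmetic is exact. The size is not known: about 9% to 26% of patient-days would be uncategorised at an assumed 1% item missingness with a mean of 0.5 to 5 symptoms, assuming independent blanks, and near zero with forced completion. Severity is minor. One safety analysis is touched; no efficacy result, alpha level or sample size depends on it.

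**What to change.** In SAP 3.8.6:

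1. Set the daily total to missing when 50% or more of the 43 items are blank, as for MADRS. This also settles the wholly blank day, for which the fill rule is undefined.
2. Otherwise keep the unrounded prorated total for the period average and the Wilcoxon test.
3. For the 0, 1, 2, 3, ≥ 4 table, use the prorated total rounded to the nearest whole number.
4. State that the daily CMH test uses those categories.

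Rounding keeps the SAP's imputation, whereas an observed count would treat blanks as absence of symptoms. The rounded value equals the observed count until 15 items are blank for k = 1, 9 for k = 2 and 7 for k = 3.

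The cost is a sentence or two in the SAP and a small change to the derivation code. The downside is that a few sparse diary days become missing.
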